5.5 INTERVENTION ALLOCATION

Consented patients' contact details will be passed to LCs who will then commence the TreatWELL personalised intervention delivered in three phases. The duration of each phase is based on individual treatment regimens (e.g. those receiving adjuvant therapy will be on the programme for a longer period). Decisions about phase completion (e.g. defining the end of post-surgical recovery) and progression will be agreed in conjunction with the CNS.

5.5.1 Withdrawal procedures

Individuals have the right to withdraw consent for participation in any aspect of this study at any time. Care from other services will not be affected at any time by declining to participate or withdrawing from the trial.

6 STUDY & SAFETY ASSESSMENTS

Adverse events including GP visits and hospital admissions will be recorded at each assessment (with the RNS and the LCs). The RNS / LCs will follow the guidelines for reporting adverse events (including serious adverse events) as written in a standard operating procedure.

In all phases participants will undergo nutritional screening using the malnutrition universal screening tool (MUST). Participants at risk of malnutrition will be referred to the NHS dietician (as per usual care) for all dietary management (but will continue with other aspects of the intervention delivered by the LCs).

7 DATA COLLECTION & MANAGEMENT

7.1 DATA COLLECTION

At each contact with the RNS (T0, T1, T2, T3) data will be collected and recorded directly onto a paper case report form (CRF) which will be comprised of a number of questionnaires:

- Physiological measures (body weight, height, waist circumference, skin fold)
- Medication usage data
- Self-reported smoking
- Self-reported alcohol intake
- The scottish physical activity questionnaire
- Six minute walk test
- The DINE questionnaire
- The multidimensional fatigue inventory (MFI-20)
- Self-reported bowel function by LARS score
- The EORTC Quality of Life questionnaires for bowel cancer patients and colorectal cancer patients

The LCs will complete a structured pro-forma after every patient contact. This will record actual values or scaled ratings on:

- Intervention start time (days after diagnosis)
- Total contact time
- Ease or difficulty of implementing the session
- Perceived fidelity to the intervention content and approach
- Extent of patient engagement, receptivity and motivation

7.2 DATA MANAGEMENT SYSTEM

Data from the CRFs and pro-formas will be entered into SPSS for analysis.

8 STATISTICS AND DATA ANALYSIS

Feasibility measures that will be assessed are programme implementation, fidelity to protocol, achieved measurements, recruitment, response, retention and adherence to programme.

Outcome measures (changes between baseline and follow up time points) will be analysed but it should be noted that these are indicative results only as this trial is not powered to show definitive results.

Data from pro-formas completed by LCs will be analysed to assess completeness of delivery and areas for improvement, and to provide contextual information (including NHS service issues) on patient engagement.

All participant interviews that take place at the end of stages 2 and 3 will be recorded, transcribed and analysed using a thematic framework approach to identify what might be considered practical and acceptable for intervention recruitment and delivery. Analysis of interview data will identify likely facilitators and barriers to conducting a full RCT.

Cost of intervention delivery will be analysed from LCs costs and other consumables.

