2 AIMS

This study aims to assess the practical aspects of delivering a lifestyle intervention programme (TreatWELL) for CRC patients undergoing potentially curative treatments in order to inform the feasibility of undertaking a randomised controlled trial (RCT) to evaluate the impact of the intervention programme on health outcomes at one year after diagnosis.

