2.1.1 Primary Research Questions

(i) What is the uptake of the proposed intervention programme during the period between diagnosis and surgery?

- What are the recruitment levels that can be achieved within the study duration and how do these vary between disease status and socio-demographic factors?
- How soon after diagnosis can patients commence the intervention programme?

(ii) Can all of the intervention components be delivered in the intervention phases?

- Can the programme be successfully implemented within the NHS setting?
- What is the actual length of time in each phase?
- What is the intervention fidelity to the TreatWELL protocol, which areas present delivery challenges and why?

(iii) What are the responses of patients to the intervention programme and evaluation measures?

- To what extent are patients able to achieve smoking, physical activity and dietary change before, during and after treatment (adherence)?
- Can the proposed evaluation measurements on behavioural and health outcomes (relevant for future RCT) be undertaken successfully?
- What is the retention rate at the end of the study period?

(iv) What are the patients' views on the intervention programme?

- How acceptable are the intervention recruitment methods, programme content, delivery, intensity and exit strategy to participants?
- What factors do patients think influence adherence?

(v) What are the intervention programme delivery costs?

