2.2.4 Acceptability of and engagement in the intervention (RQ iv)

This will be determined by in-depth qualitative interviews (guided by Stirling University) transcribed and analysed using a thematic framework approach. A random sample of 1 in 3 participants (n=10) stratified by degree of engagement with the intervention will be invited for interview at the end of phase 2 and again (another 10 participants) at the end of phase 3. These interviews will explore patient views on recruitment methods and timing, assessment procedures, programme content, activity and body weight goals, delivery, duration, intensity and exit strategy. In addition, participants will be asked to discuss factors influencing adherence including personal beliefs, motivation, family members, social and NHS staff support.

Interviews will also be conducted the two lifestyle coaches and the research nurse, who are members of the research team, for their views and feedback of the intervention delivery.

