3 STUDY DESIGN

This study will be a single arm, single centre feasibility study of the TreatWELL intervention programme.

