5 PARTICIPANT SELECTION AND ENROLMENT

5.1 IDENTIFYING PARTICIPANTS

When patients receive their cancer diagnosis they are routinely referred to the clinical nurse specialist (CNS) to discuss treatment and care plans. At present, the CNS provides brief (2-3 minutes) lifestyle advice. During the study, the CNS will inform eligible patients about the study and endorse the importance of the study for helping achieve lifestyle change in the pre

surgery period. Pateints will be asked if they would be interested in taking part, or in hearing more about the study, and those interested will be introduced to the TreatWELL research nurse (RNS) (up to 10 days of diagnosis) who will be present at the clinic.

If patients indicate to the CNS that they are happy to be introduced to the research nurse, the RNS will provide face to face verbal and written information about the study and request permission to re-contact patients within 48 hours, allowing at least 24 hours to consider taking part in the study. Patients details will be collected by the RNS on a response form. Information will include a participant information sheet and an invitation and endorsement letter from the lead CRC clinician for Tayside..

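### The interviews are to identify barriers to a full RCT, but no listed question, topic or record covers randomisation or a usual-care arm, so the consent rate describes a non-randomised offer only

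*Protocol*

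**What the plan says.** Section 2 (Aims) sets the purpose: the practical aspects of delivery are assessed "in order to inform the feasibility of undertaking a randomised controlled trial (RCT) to evaluate the impact of the intervention programme on health outcomes". Section 8 turns part of this into a specific output: "Analysis of interview data will identify likely facilitators and barriers to conducting a full RCT".

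Section 3 fixes the design: "This study will be a single arm, single centre feasibility study of the TreatWELL intervention programme". Under section 5.5, the lifestyle counsellors start the programme with every patient who consents. There is no comparator.

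Research question (i) in section 2.1.1 asks "What is the uptake of the proposed intervention programme during the period between diagnosis and surgery", with the sub-question "What are the recruitment levels that can be achieved within the study duration and how do these vary between disease status and socio-demographic factors".

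Section 2.2.4 lists the patient interview topics: "These interviews will explore patient views on recruitment methods and timing, assessment procedures, programme content, activity and body weight goals, delivery, duration, intensity". The list ends with the exit strategy, and factors that influence adherence are added. Ten participants are invited at the end of phase 2 and another ten at the end of phase 3. The two lifestyle coaches and the research nurse are interviewed about delivery of the intervention. Section 5.4 records reasons for declining, and demographics, from patients who are willing to give them.

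Sections 4.1 and 8.1 expect 60 diagnoses in 5 months, 48 eligible patients and 34 (71%) who agree.

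**The concern.** An RCT of this programme would ask patients, soon after a cancer diagnosis, to accept allocation by chance, possibly to usual care. That is a different request from being offered the programme outright. Some patients who want the programme may not want a chance of it.

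Section 8 says the interviews will show what helps and hinders a full RCT. Reluctance to be randomised, and dissatisfaction with a usual-care arm, are barriers that arise only in an RCT. If nothing in the study asks about them, that part of the output has no planned data. A later trial team would then have a consent rate for the certain offer and nothing with which to adjust it. The practical stake is the planned accrual rate of the RCT, and hence its duration or number of centres.

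**Working it through.** **Step 1. Reproduce the plan's figure** (sections 4.1 and 8.1).
- Eligible: 48/60 = 80%.
- Consent among eligible: 34/48 = 70.8%, and 48 × 0.71 = 34.08. The stated 71% and 34 agree.
- Accrual: 34/5 = 6.8 per month.
- If exactly 34 of 48 consent, the 95% interval is 56.8% to 81.8% (Wilson) or 55.9% to 83.0% (Clopper-Pearson). This is sampling error for consent to the programme. It contains no allowance for the step from a certain offer to a randomised one.

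**Step 2. Look for a source on randomisation or a usual-care arm.**

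| Source | Who is asked | Listed content | Randomisation or usual-care arm listed? |
|---|---|---|---|
| Research questions (2.1.1) | – | Uptake, timing, delivery, adherence, measures, retention, acceptability, cost | No |
| Patient interviews (2.2.4) | 10 + 10 enrolled participants | Recruitment methods and timing, assessments, programme features, adherence factors | No |
| Staff interviews (2.2.4) | Two coaches, research nurse | Delivery of the intervention | No |
| Reasons record (5.4) | Decliners who volunteer them | Reasons and demographics | No |

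Every patient interviewed will have accepted, and been given, a guaranteed programme. On the plan's figures 48 − 34 = 14 eligible patients decline. They are declining that same guaranteed offer, so their reasons cannot reveal reluctance to be randomised unless they are asked.

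**Step 3. What the gap could mean for accrual.** The documents give no rate of consent to randomisation. Let *f* be the ratio of RCT consent to programme consent. The range of *f* is an assumption and nothing in the documents anchors it.

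RCT consent = (34/48) × *f*. Accrual per month = 6.8 × *f*, with the same flow of eligible patients.

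| Assumed *f* | RCT consent | Patients per month |
|---|---|---|
| 1.0 | 70.8% | 6.8 |
| 0.9 | 63.8% | 6.1 |
| 0.8 | 56.7% | 5.4 |
| 0.7 | 49.6% | 4.8 |
| 0.6 | 42.5% | 4.1 |
| 0.5 | 35.4% | 3.4 |

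Across the assumed range, accrual varies by a factor of two. The study as listed collects nothing that would help to choose *f*.

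**The case against.** The strongest reply is that a single-arm stage before a randomised one is a legitimate, declared choice, and that the aim is only to inform RCT feasibility through practical aspects of delivery. None of the five research questions asks about randomisation, and the questions that are asked have data sources. Much of what the interviews cover, such as recruitment methods, assessment burden, intensity and staff support, also bears on an RCT. The sentence just before the one quoted from section 8 concerns the recruitment and delivery of the intervention, which suggests a narrower intention.

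Most of this stands, and it rules out several stronger readings that a reader might infer:

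- *The study cannot meet its aim, or the section 8 output has no data at all.* Not supported. Delivery, measurement, retention, timing, acceptability and cost are all addressed. Only the part on randomisation and the usual-care arm is missing.
- *Nobody will be asked about randomisation.* This cannot be shown. The interview guide and the response form are not in the protocol, and the recruitment heading is broad. What can be said is that no listed topic covers it.
- *The study will overstate RCT recruitment.* Not supported. The protocol never says that observed uptake will serve as the RCT rate. Question (i) already speaks of uptake of the programme, and section 8.1 names effect sizes and sample size as what the study informs.
- *Endorsement by the nurse specialist and the lead clinician biases uptake.* An RCT could use the same endorsement. The difference that matters is guaranteed allocation.

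What the reply does not remove is the section 8 sentence itself. It concerns conducting a full RCT, it goes beyond the sentence before it, and the listed content does not reach a barrier that is specific to an RCT.

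**Conclusion.** The point holds in a limited form. The protocol says it will identify barriers to a full RCT, but as listed it plans no evidence on willingness to be randomised or on acceptability of a usual-care arm. The expected consent rate of 34/48 (71%) is uptake of a non-randomised offer. It could overstate RCT consent if someone later reads it as such.

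The direction is plausible but not documented, and the size is unknown. The span of 35% to 71%, or 3.4 to 6.8 patients a month, rests wholly on the assumed ratio of 0.5 to 1.0 and an unchanged flow of 48 eligible patients in 5 months. It shows why the question is worth asking and is not an estimate.

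This is a cheap improvement to a sound type of study. It does not call for a randomised design at this stage.

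**What to change.** 1. **Section 2.2.4:** add willingness to be randomised and acceptability of a usual-care arm to the patient interviews at the end of phases 2 and 3, and to the research nurse interview.
2. **Sections 5.1 and 5.4:** add one optional item to the response form for patients who meet the research nurse, and to the reasons record for decliners willing to answer. It would ask whether they would have taken part had chance decided between the programme and usual care.
3. **Section 8:** report the recruitment rate as uptake of a non-randomised offer, beside the stated willingness to be randomised.
4. **If the items are not added:** narrow the section 8 sentence on RCT barriers to delivery and measurement.

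The cost is one question on existing forms, two interview topics and some wording, with a slightly longer first contact. The answers are hypothetical, and interviewees give them after receiving the programme, so they are only a guide. Precision is also limited: if all 34 acceptors answered and half said yes, the approximate 95% interval would be 50% ± 1.96 × √(0.25/34) = 50% ± 17 points. Patients who decline at the nurse specialist stage never meet the research nurse and would not be reached.

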8.1 SAMPLE SIZE CALCULATION

This is a feasibility study to test practical aspects of study design which will help inform the calculation of effect sizes required for a subsequent RCT. It is estimated that within the 5 month recruitment period that 60 patients will be diagnosed with CRC and begin treatment. Based on our previous lifestyle trial in CRC patients¹³ it is estimated that 48 of 60 patients will meet the inclusion criteria and 34 (71%) will agree to participate. These numbers should

provide sufficient data on feasibility measures. Feasibility studies are not designed to test hypotheses but to provide data to inform sample size required to show significant differences in health outcome variables in a fully powered RCT.

9 STUDY MANAGEMENT AND OVERSIGHT ARRANGEMENTS

9.1 STUDY MANAGEMENT GROUP

All investigators and the study manager will be invited to participate in study management group (SMG) meetings (face to face or by teleconference) and will be responsible for the day to day running of the study

9.2 STUDY MANAGEMENT

The study will be led by the PIs. A study manager, will oversee the day to day running of the study, will be responsible for checking the CRFs for completeness, plausibility and consistency and will be accountable to the PIs and the SMG. Any queries will be resolved by the PIs or other member of the study team.

A study-specific delegation log will be prepared, detailing the responsibilities of each member of staff working on the study.

Budgeting control will be overseen by the divisional research manager.

9.3 INSPECTION OF RECORDS

The institutions involved in the study will permit study related monitoring, audits, and REC review. The PIs agree to allow the sponsor or, representatives of the sponsor, direct access to all study records and source documentation.

10 GOOD CLINICAL PRACTICE

10.1 ETHICAL CONDUCT OF THE STUDY

The study will be conducted in accordance with the principles of good clinical practice (GCP). No investigational medicinal products are being tested in this study and therefore it is not regulated by the UK's Medicines and Healthcare products Regulatory Agency.

In addition to sponsorship approval, a favorable ethical opinion will be obtained from the East of Scotland Research Ethics Service and appropriate NHS R&D approval will be obtained prior to commencement of the study.

Advice and support on governance and GCP will be provided by the Tayside Clinical Trials Unit. TreatWELL will make use of the University of Dundee's Standard Operating Procedures for tasks such as obtaining informed consent, managing and archiving data, training and how to handle breaches of GCP.

All staff involved with patient care during the study will undergo GCP training (CNS, RNS and LCs).

10.1.1 Confidentiality

All evaluation forms, reports, and other records will be identified in a manner designed to maintain participant confidentiality. All records will be kept in a secure storage area with limited access to study staff only. Clinical information will not be released without the written permission of the participant, except as necessary for monitoring and auditing by the sponsor or its designee. The PIs and study staff involved with this study will not disclose or use for any purpose other than performance of the study, any data, record, or other unpublished, confidential information disclosed to those individuals for the purpose of the study. Prior

written agreement from the sponsor or its designee will be obtained for the disclosure of any said confidential information to other parties.

10.1.2 Data Protection

The PIs and study staff involved with this study will comply with the requirements of the Data Protection Act 1998 with regard to the collection, storage, processing and disclosure of personal information and will uphold the Act's core principles. The PIs and study staff will also adhere, if appropriate, to the current version of the NHS Scotland Code of Practice on Protecting Patient Confidentiality. Access to collated participant data will be restricted to the PIs and appropriate study staff.

Computers used to collate the data will have limited access measures via user names and passwords.

Published results will not contain any personal data that could allow identification of individual participants.

10.1.3 Insurance and Indemnity

The University of Dundee is sponsoring the study.

Insurance The University of Dundee will obtain and hold a policy of Public Liability Insurance for legal liabilities arising from the study.

Where the study involves University of Dundee staff undertaking clinical research on NHS patients, such staff will hold honorary contracts with Tayside Health Board which means they will have cover under Tayside's membership of the CNORIS scheme.

Indemnity The sponsor does not provide study participants with indemnity in relation to participation in the study but has insurance for legal liability as described above.

11 STUDY CONDUCT RESPONSIBILITIES

11.1 PROTOCOL AMENDMENTS, DEVIATIONS AND BREACHES

The PIs will seek approval for any amendments to the protocol or other study documents from the sponsor, REC and NHS R&D office. Amendments to the protocol or other study documents will not be implemented without these approvals.

In the event that the PIs need to deviate from the protocol, the nature of and reasons for the deviation will be recorded in the CRF, documented and submitted to the sponsor. If this necessitates a subsequent protocol amendment, this will be submitted to the sponsor for approval and then to the REC and NHS R&D office for review and approval.

In the event that a serious breach of GCP is suspected, this will be reported to the sponsor immediately using the form "Notification to Sponsor of Serious Breach or Serious Deviation".

11.2 STUDY RECORD RETENTION

Data will be held according to GCP requirements. All data will be held for a minimum of five years from completion of the study.

11.3 END OF STUDY

The study will be considered closed when the last piece of follow up information has been collected for the last participant. The sponsor and / or the PIs have the right at any time to terminate the study for clinical or administrative reasons.

The end of the study will be reported to the sponsor and REC within 90 days, or 15 days if the study is terminated prematurely. The PIs will ensure that any appropriate follow up is arranged for all participants.

A summary report of the study will be provided to the sponsor and REC within 1 year of the end of the study.

12 REPORTING, PUBLICATIONS AND NOTIFICATION OF RESULTS

12.1 AUTHORSHIP POLICY

Ownership of the data arising from this study resides with the study team and their respective employers. On completion of the study, the study data will be analysed and tabulated, and a clinical study report will be prepared.

12.2 PUBLICATION

The publication policy will be drafted by the SMG and will state the principles for publication, describe a process for developing output and contain a map of intended outputs with a timeline for delivery. The publication policy will respect the rights or all contributors to be adequately represented in outputs (e.g. authorship and acknowledgements) and the study to be appropriately acknowledged. Authorship of parallel studies initiated outside the SMG will be according to individuals involved in the study but must acknowledge the contribution of the SMG.

